8.2. Outcomes and Analysis

8.2.1. HRM

The following outcomes will be assessed:

- Study recruitment, including practicalities and acceptability of conducting tests prior to treatment initiation (time to test) and site differences. Partial information will be reported, increasing understanding of acceptability.
- Successful completion of test meal during HRM.
- Successful completion of questionnaires for PROMs data.
- Drop-out between initial and post-treatment tests, using information from qualitative interviews to understand barriers.
- Description of changes to diagnostic yield (categorical data) as a result of solid swallows compared to water swallows during HRM, classified in line with routine clinical practice using CCv4.0^{8,15}.
 - This will be described both pre- and post-treatment, providing insight into possible effect size of change in motility classification in EoE (currently unknown) for future study.
 - o Differences will be described in relation to previous treatment exposure and overall symptom status from PROMs.
 - Changes will be described in those recruited with a new diagnosis of EoE versus those recruited as treatment refractory.
- Temporal relationships between patient-reported symptoms and abnormalities identified on HRM will be defined using the oesophageal dysfunction symptom index (D-SI), whereby number of symptoms associated with oesophageal dysfunction is divided by total number of symptoms¹⁶ and numbers in whom typical symptoms are reproduced will be reported.

IRAS ID: 299013

8.2.2. pH/impedance monitoring

The following outcomes will be assessed:

- Recruitment, including practicalities of conducting tests prior to treatment initiation (time to test) and site differences.
- Drop-out between initial and post-treatment tests, using information from qualitative interviews to understand barriers.
- Tolerance of a 24-hour test by patients with EoE.
- Description of mucosal impedance/MNBI as a marker of ongoing inflammation in relation to eosinophilia pre- and post-treatment, with quantitative outcomes described by confidence intervals and treated as preliminary findings.
 - Differences will be described in relation to previous treatment exposure and overall symptom status from PROMs.
- Presence of reflux disease, described using the Lyon Criteria¹².
- Descriptive comparison of histological findings (EoE histologic scoring system/HSS¹⁷) to mucosal impedance results.

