6. STUDY PROCEDURES

6.1.Covid-19 (Sars-CoV-2)

Local regulations (CDDFT and UCLH) will be adhered to regarding the Covid-19 pandemic.

6.2.Pre-treatment tests

IRAS ID: 299013

6.2.1. Visit 1

PROMs will be collected using three validated questionnaires completed by the patient. These will assess dysphagia, reflux burden and oesophageal hypervigilance and anxiety using the Brief Esophageal Dysphagia Questionnaire/BEDQ¹⁰, Reflux Disease Questionnaire/RDQ¹¹ and Esophageal Hypervigilance and Anxiety Scale/EHAS⁹ respectively.

HRM: HRM involves placement of a nasogastric catheter. Testing will follow standard procedures with additional provocation tests:

- Assessment of 5 mL water swallows
- Rapid drink challenge 200 mL water drunk continuously through a straw. This is used to further assess lower oesophageal sphincter relaxation and oesophageal body pressurisation
- Solid test meal 200g rice eaten to assess oesophageal function using a physiologically relevant test meal

Symptomatic episodes during swallowing will be recorded to determine if reported symptoms correspond with abnormal HRM events, thus assessing the clinical relevance of motility findings. Findings will be classified using the Chicago Classification (CCv4.0)⁸.

pH/impedance monitoring: Following PROMs and HRM, 24-hour ambulatory pH/impedance monitoring using a nasogastric catheter will commence. This involves placement of a second naso-gastric pH/impedance catheter. Testing will follow standard procedures. Patients will be provided with a paper diary to complete and an explanation will be given as to how to use the ambulatory recorder.

6.2.2. Visit 2

Participants will return the ambulatory recorder the following day (24 hours after initiation of ambulatory pH/impedance test).

Individuals will begin treatment course after physiology tests have been performed. Treatment will be standard care (usually locally acting steroids and/or proton pump inhibitors), decided upon by patient and clinician (study does not influence treatment choice). Those patients with an established diagnosis of EoE who are in symptom remission may not begin new treatment course and in this case would only participate in initial tests.

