8.2.4. Cross-study analysis

Information on symptoms, oesophageal muscle function and inflammation identified within the study will be collated to provide preliminary insight into potential relationships. This includes reported symptom types and severity (PROMs data⁹⁻¹¹), motility findings (HRM), mucosal impedance, results from standard care (endoscopy, histology) and disease duration, in relation to treatment. This will inform on the practicalities of collecting meaningful multi-factorial data, with a view to future work defining factors relating to EoE disease profiles. Patient numbers in whom objective physiology and subjective symptoms relate will provide preliminary insight into proportions of individuals who could, in the future, respond to treatment targeted at the specific pathophysiology.

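### The D-SI uses symptomatic moments only, so without the background rate of abnormal swallows a high value cannot show that motility findings are clinically relevant

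*Protocol*

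**What the plan says.** Section 2.2, Objective 1, asks for a description of motility when solid food is swallowed and an assessment of motility during symptomatic episodes while eating. Section 6.2.1 (Visit 1) adds a purpose: "Symptomatic episodes during swallowing will be recorded to determine if reported symptoms correspond with abnormal HRM events, thus assessing the clinical relevance of motility findings".

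Section 8.2.1 says the temporal relationship is to be defined by the D-SI, "whereby number of symptoms associated with oesophageal dysfunction is divided by total number of symptoms". The same sentence adds that "numbers in whom typical symptoms are reproduced will be reported". Elsewhere in 8.2.1, under diagnostic yield from solid versus water swallows, "Differences will be described in relation to previous treatment exposure and overall symptom status from PROMs".

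Section 8.2.4 looks across the study: "Patient numbers in whom objective physiology and subjective symptoms relate will provide preliminary insight into proportions of individuals who could". The rest of that sentence concerns future response to therapy aimed at the underlying mechanism. The section gives no rule for deciding when physiology and symptoms are related, and it does not mention the D-SI.

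Section 6.4.1 repeats manometry and the questionnaires two to four months after treatment. No comparison of the D-SI between visits is stated.

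**The concern.** The D-SI has no term for swallows without symptoms, whether normal or abnormal. A patient with abnormal motility on nearly every swallow will have nearly every symptom coincide with an abnormal swallow, whether or not motility causes the symptoms. To say that a motility finding is clinically relevant, one must know whether abnormality is commoner on symptomatic than on symptom-free swallows. The named measure supplies only the first half of that comparison.

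What is at stake is the reading of the symptom result, and of any section 8.2.4 count that draws on it. Such a count would be inflated most in patients with the most abnormal motility, and it is meant to suggest how many people might benefit from targeted treatment in future work.

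**Working it through.** **Inputs from the protocol.** The D-SI definition (8.2.1) and the recruitment target of 60 (8.1). The protocol states no expected D-SI, cut-off, abnormal-swallow rate or symptom count, so there is no figure of its own to reproduce.

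**Assumptions, not in the protocol.** A share p of swallows is abnormal, with p from 0.1 to 0.8. A patient reports k symptoms. A symptom counts as associated when it falls on an abnormal swallow. A 50% cut and a meal of 30 swallows are used for illustration only.

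**Step 1: value under no association.** Each symptom falls on an abnormal swallow with probability p, so the associated count is Binomial(k, p) and E[D-SI] = kp/k = p.

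**Step 2: chance of D-SI ≥ 50% under no association.** This is P(X ≥ k/2) with X ~ Binomial(k, p). For k = 1 it is p. For k = 2 it is 1 − (1 − p)². For k = 3 it is 3p²(1 − p) + p³.

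| p | k = 1 | k = 2 | k = 3 | k = 4 | k = 10 |
|---|---|---|---|---|---|
| 0.1 | 10% | 19% | 3% | 5% | 0.2% |
| 0.3 | 30% | 51% | 22% | 35% | 15% |
| 0.5 | 50% | 75% | 50% | 69% | 62% |
| 0.7 | 70% | 91% | 78% | 92% | 95% |
| 0.8 | 80% | 96% | 90% | 97% | 99% |

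If all 60 participants had four symptoms each, the number reaching 50% by chance would be about 3 at p = 0.1 (60 × 0.052), 41 at p = 0.5 (60 × 0.688) and 58 at p = 0.8 (60 × 0.973).

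**Step 3: the same D-SI at different background rates.** Take 30 swallows, 4 of them symptomatic, 3 of those 4 abnormal. The D-SI is 3/4 = 0.75 throughout. The chance of 3 or more coincidences (hypergeometric) is:

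- 3 abnormal swallows of 30: 0.001
- 6 of 30: 0.018
- 9 of 30: 0.069
- 15 of 30: 0.30
- 21 of 30: 0.66
- 24 of 30: 0.83

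The two-by-two counts separate these cases:

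- With 6 abnormal swallows, symptom-free swallows are abnormal in 3/26 = 12%. The symptom rate is 3/6 = 50% after abnormal swallows and 1/24 = 4% after normal ones.
- With 24 abnormal swallows, symptom-free swallows are abnormal in 21/26 = 81%. The symptom rates are 3/24 = 12.5% and 1/6 = 17%, which is no sign of a link.

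**Step 4: behaviour if the D-SI is shown at both visits.** Start from 4/10 = 0.40. Losing five unrelated symptoms gives 4/5 = 0.80. Losing three associated symptoms gives 1/7 = 0.14. Halving both kinds gives 2/5 = 0.40. Losing all symptoms gives 0/0, which is undefined.

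**The case against.** The best defence is that the D-SI answers what Objective 1 literally asks, which is motility during symptomatic episodes. That is fair for Objective 1. Section 6.2.1 goes further, to clinical relevance, and there the comparison with symptom-free swallows is needed.

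The D-SI also does not stand alone: section 8.2.1 counts patients whose typical symptoms are reproduced and describes motility yield against the questionnaires. This is correct, but neither output corrects swallow-level coincidence for chance.

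A reader might infer two stronger points, and the protocol supports neither:

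- **That section 8.2.4 counts chance coincidence as a relation between physiology and symptoms.** It names neither the D-SI nor a cut-off, and its inputs also include questionnaires, impedance, endoscopy, histology and disease duration. Use of the D-SI there is plausible but not a stated rule.
- **That the D-SI is the planned measure of treatment change and loses the responders.** The text on describing results before and after treatment belongs to diagnostic yield. The D-SI indexes association, so a higher value is not a worse outcome, and symptom burden is followed by the repeated questionnaires.

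Two further objections stand in part. What counts as associated (time window, type of dysfunction) is left to the cited method paper, which was not available here; a stricter definition would lower the effective p. Handling of tests with no symptoms may sit in an analysis plan not shown. Neither removes the missing background rate from the definition the protocol adopts.

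**Conclusion.** The point holds in a limited form. As defined in section 8.2.1, the D-SI has a no-association expectation equal to the abnormal-swallow rate, so a high value alone cannot establish clinical relevance or a relation between physiology and symptoms. This follows from the definition once symptoms are taken to fall on swallows independently of swallow status.

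The size rests on assumed values. The problem is large when most swallows are abnormal (97% chance of reaching the illustrative cut at p = 0.8 with four symptoms) and small when few are abnormal and symptoms are several (5% at p = 0.1 with four, 0.2% with ten).

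The consequence is bounded: this is a descriptive feasibility study that claims preliminary insight, and no test or treatment decision in the protocol depends on the D-SI. The change is still worth making because it costs little and makes the symptom result interpretable.

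**What to change.** - **Section 8.2.1.** Keep the D-SI. For each participant and visit, report beside it the swallow-level counts: symptomatic or symptom-free by abnormal or normal. From these give the proportion of symptom-free test-meal swallows with dysfunction, and the symptom rate after abnormal and after normal swallows.
- **Section 8.2.4.** State that any count drawing on the D-SI will be interpreted against that background rate.
- **Both visits.** If the D-SI is shown before and after treatment, give its numerator, its denominator and the number of swallows. Report participants with no symptoms as a separate group so that they are not dropped as 0/0. The number of swallows matters because symptom counts also fall when less of the meal is eaten.

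One tempting shortcut should be avoided: classing a participant as linked whenever the abnormal proportion is merely higher on symptomatic than on symptom-free swallows. With one symptom its chance rate is again p (30%, 50%, 70% for p = 0.3, 0.5, 0.7). With 9 of 30 swallows abnormal and three symptoms it is 1 − C(21,3)/C(30,3) = 1 − 1330/4060 = 67%, against 840/4060 = 21% for D-SI ≥ 50%.

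The cost is a few sentences and slightly more tabulation. The manometry recording and the recorded symptomatic episodes already hold the data, so no extra test, visit or participant is needed. The downside is that the apparent link between symptoms and motility may look weaker.

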8.2.3. Qualitative interviews

An inductive approach to analysis will be used to identify themes from the data corpus, drawing on the six phases of thematic analysis outlined by Braun and Clark¹⁸. Broadly, the following pre-defined topics will be explored: impact of living with EoE, acceptability of routine follow-up investigations once a diagnosis of EoE has been made (endoscopy, biopsies, imaging) and the additional testing performed as part of this study (HRM and pH/impedance monitoring). Further exploration of influences on acceptability will be explored, including whether participants felt that tests provided realistic insight into their problems, cultural factors surrounding the test meal and socio-economic factors on how people manage on a daily basis with a condition that affects eating. Data collected will also be used to understand the recruitment patterns of the study.

NVivo software will be used to organise and analyse pseudonymised interview transcripts. Codes used to organise the data will be refined iteratively and degree of saturation will be assessed in order to report on the extent to which interviews captured participant views. Prior to processing, themes will be discussed with colleagues to ensure validity and reduce the impact of interpretation bias.

8.2.4. Cross-study analysis

Information on symptoms, oesophageal muscle function and inflammation identified within the study will be collated to provide preliminary insight into potential relationships. This includes reported symptom types and severity (PROMs data⁹⁻¹¹), motility findings (HRM), mucosal impedance, results from standard care (endoscopy, histology) and disease duration, in relation to treatment. This will inform on the practicalities of collecting meaningful multi-factorial data, with a view to future work defining factors relating to EoE disease profiles. Patient numbers in whom objective physiology and subjective symptoms relate will provide preliminary insight into proportions of individuals who could, in the future, respond to treatment targeted at the specific pathophysiology.

9. DATA MANAGEMENT AND CONFIDENTIALITY

9.1.Data Management

Clinical data pertaining to an individual participant will be stored within their CRF. Members of the study team involved in data entry into the CRF will receive appropriate training. A copy of each CRF will remain at the study site (CDDFT or UCLH) and a copy scanned, emailed from nhs.net to nhs.net account and stored in the Trial Master File.

Patient data will remain on NHS computers and a Microsoft Excel spreadsheet will be used to collate information from the CRF. Any electronic transfer of data will be via encrypted email accounts (nhs.net to nhs.net).

An external body (UK Transcription Ltd) will be used for transcription of data collected from participant interviews. Audio files will be anonymised prior to being transferred to UK Transcription Ltd. A non-disclosure agreement is in place, including the relevant data protection safeguards in line with GDPR. Once transcribed, audio data from recorded interviews will be deleted.

9.2.Confidentiality

The Newcastle upon Tyne Hospitals NHS Foundation Trust is the sponsor for the study and will act as the data controller. Research will be conducted in line with Caldicott Principles, General Data Protection Regulation (2018) and GCP. Encrypted, password-protected NHS IT devices will be used within local sites. Physical records other than those forming the site files will be scanned, saved and destroyed. Unique, anonymised identification codes will be used for study information leaving an NHS device (i.e. interview transcripts).

9.3. Missing Data and Data Queries

Any self-evident corrections made will be documented in the Trial Master File and will be approved by the CI. Data queries and subsequent changes made will be documented in an audit trail. Any changes will be initialled, dated and explained where necessary.

10. SAFETY REPORTING

10.1. Reporting Adverse Events

HRM and 24-hour pH/impedance investigations are low risk investigations conducted in routine practice for indications other than EoE. Procedure risks will be discussed in line with routine practice. The sponsor would be notified of any adverse events occurring during the study period including the patient ID, event, review of causality, whether it is resolved/ongoing. If deemed to have occurred as a result of the study, the adverse event will be reported on local incident reporting systems.

Any adverse events occurring will be recorded in the adverse events log and the participant's CRF and will also be documented within the Trial Master File. Details kept

will include the event, date and time, timeframe in which the event occurred, severity, actions taken, relationship of the event to the study and those involved in the event.

Any Serious Adverse Event (SAE) occurring as a result of the study will be reported by the CI to the Research Ethics Committee (REC) within 15 days of becoming aware of the event. The National Health Service Health Research Authority Non-CTIMP Safety Report to REC form should be used to do this. Any SAE will also be included in the Annual Progress Report to the REC.

11. STUDY MANAGEMENT & SPONSOR OVERSIGHT

11.1. Sponsorship, Monitoring and Auditing Arrangements

The CI or research fellow will monitor the informed consent process to ensure that consent forms are appropriately counter signed at both sites. The study team will also conduct internal monitoring to ensure the study is run in line with GCP. The study may fall under the sponsor's QA audit programme as per NJRO-QA-SOP-001 and data will be made available if requested.

12. STUDY CONDUCT RESPONSIBILITIES

12.1. Protocol Amendments

Protocol amendments must be reviewed and approved by the CI, PIs and the study team.

12.2. Management of Protocol Non Compliance

Non-compliances identified will be reported to the Sponsor (Newcastle upon Tyne Hospital NHS Foundation Trust) in a timely manner.

12.3. Serious Breach Requirements

A serious breach is defined as something that is likely to significantly effect:

- The physical or mental safety of participants; or
- The scientific value of the study

12.4. Study Retention Record

All documents will be kept for a minimum of 5 years from the study end point. Permission from the sponsor will be sought before any information is destroyed.

12.5. End of Study

End of study is defined as the final visit of the last participant. The study can be terminated by the investigators or sponsor at any time for clinical or administrative reasons.

12.6. Continuation of Treatment Following End of Study

Not applicable.

12.7. Insurance and Indemnity

Newcastle University will cover the indemnity for the design of the research. Management and conduct of the study will be covered by the NHS.

13. TRIAL FUNDING

Funding for this study has been obtained from the National Institute for Health Research's (NIHR) Integrated Clinical Academic (ICA), Clinical Doctoral Research Fellowship (CDRF) scheme (NIHR302158).

14. PUBLICATION AND DISSEMINATION PLANS

Quarterly meetings with the study advisory group will ensure regular updates on study output. Study findings will be disseminated as follows:

- Events: Two dissemination events (North East, London) for participants and members of the advisory group. As a rare condition, many have never met someone else with EoE. This will therefore provide an opportunity for people to connect and support groups to be established.
- Presentation: At events specifically for people affected by EoE (i.e. EOS Network) and within the GI Physiology community via the Association of Gastrointestinal Physiologists (AGIP).
- Conference presentations: One major gastroenterology conference in years two and three, including the British Society of Gastroenterology's annual conference, enabling dissemination to NHS professionals.
- Publications: Open-access, peer-reviewed publications to contribute to scientific and clinical communities with contingent titles of: Feasibility of enhanced motility assessment in EoE using HRM with solid test meal, Integration of mucosal impedance in the EoE assessment pathway, Qualitative findings in EoE from existing standard of care with augmented physiological assessments.

16. APPENDIX

16.1. Brief Esophageal Dysphagia Questionnaire

Brief Esophageal (oesophageal) Dysphagia Questionnaire

We would like to ask about your dysphagia (difficulty swallowing) symptoms over the past 2 weeks (14 days) and two experiences over the last 12 months. Please think about your symptom experiences and choose the best answer.

Over the past 14 days, on average, how often have you had the following? If your response falls between two categories, please make your best guess. If you are unable to eat the type of food in the question, please choose "Cannot eat this". Please place a tick in the relevant box.

		0	1	2	3	4	5
	Cannot Eat This	Rarely/ Never	Once or twice a month	1-2 times per week	3-5 times per week	Daily or almost daily	Several times per day
Trouble eating solid food (meat, bread, vegetables)				·			
Trouble eating soft foods (yogurt, jelly, pudding*)							
Trouble swallowing liquids							
Pain while swallowing	-						
Coughing or choking while swallowing foods or liquids	-						

Over the past 14 days, on average, how would you rate your discomfort or pain during swallowing? If you are unable to eat the type of food, please choose "Cannot eat this".

	Cannot Eat This	0 None	1 Very Mild	2 Mild	3 Moderate	4 Moderately Severe	5 Severe
Eating solid food (meat, bread, vegetables)							
Eating soft foods (yogurt, jelly, pudding*)							
Drinking liquids							

^{*}Pudding refers to a soft dessert such as mousse

Approximately how many times in	the past 12 months have you -	
Had food stuck in your throat or o Had to visit the emergency room* *Accident and Emergency Department,	because of food stuck in your thr	
Participant Initials	Screening Number	Participant Number

IRAS ID: 299013

